## 7 Statistical Plan

### 7.1 Statistical Methods

All patients meeting the eligibility criteria, and who started treatment, will be considered evaluable for the 2 year RFS rate endpoint. The proportion of 2 year RFS rates (along with the 95% confidence interval) will be estimated within each arm by the number of patients who are recurrence-free and alive at 2 years divided by the total number of evaluable patients in each arm, and compared using a chi-squared test.

Clinical data regarding recurrence-free survival (RFS) will be utilized for development of the metformin sensitivity index. Data collected will be summarized using descriptive statistics, including mean and standard deviation and median and inter quartile range for continuous variables, and using frequencies and percentages for categorical variables. Logistic regression models will be used to assess the impact of metformin sensitivity index metrics, treatment, and the interaction between the metformin sensitivity index metrics and treatment on the 2 year RFS status as the outcome of interest.

Adverse events (AEs) will be compared between metformin and placebo using CTCAE version 4. To evaluate the AE profiles associated with each intervention arm, the maximum grade for each type of AE will be recorded for each participant and frequency tables will be reviewed to determine the overall patterns. The number and severity of AEs (overall and by intervention group) will be tabulated and summarized across all grades. Chi-square tests will be used to compare the AE rates between metformin and placebo.

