## 2 Study Objectives

Primary objective for pilot study:

1. To evaluate the feasibility of patient randomization, accrual, and tissue collection in a pilot study of metformin versus observation following resection of stage IA-IIIA lung squamous cell cancer for patients.
2. To compare the 2-year recurrence free survival (RFS) rate between metformin and observation.

[figure not shown]
Secondary objective(s) for pilot study:

1. To develop the metformin sensitivity index based on iPS cell lines from the first 20 patients randomized to the metformin arm.
2. To apply the metformin sensitivity index on the remaining 25 patients randomized to metformin and the 45 observation patients (70patients total) to compare the 2-year RFS rate between metformin-sensitive and metformin-not-sensitive patients
3. To compare adverse events between metformin and observation arms using CTCAE version 4.

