## 3 Study Design

### 3.1 General Design

Patients will be identified and enrolled from Thoracic Surgical Clinics. Patients will undergo surgical resection with the collection of tumor tissue, normal lung tissue, blood, and skin biopsies. For patients enrolled in the study that were found to have stage IA-IIIA SCC, starting less than 90 days from the time of surgery, patients will be randomized to receive either 850 mg po BID of metformin or observation. Metformin dosing will include a 4 week ramp up of 850 mg po daily prior to starting the BID dose, for a total of 6 months of Metformin. Patients will be followed for 2 years from the time of surgery to evaluate 2-year RFS. We plan to randomize a total of 100 patients (50 per arm), such that 90 patients are evaluable for the primary endpoint.

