### **5.4 Preparation and Administration of Study Drug**

The metformin will be prepared by the Mayo Clinic Pharmacy, Research Support. At the time of the visit it will be distributed by the study team. Subsequent refills will be mailed to the subject by the pharmacy. The patient will receive dosing instruction by the study team.

[name], RPh  
Mayo Clinic Pharmacy, Research Support  
[name] or [contact]  
[[contact]](mailto:[contact])

Mayo Clinic Pharmacy, Research Support  
[name] or pager [name]  
[[contact]](mailto:[contact])

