### **6.3 Visit 3**

At the time of the subjects follow up (less than 90 days from the time of surgery) the subject will be seen by the study team. Eligibility criteria will be assessed and if the subject is still eligible they will be randomized and receive their study treatment (metformin or observation).

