### **6.5 Half Yearly Follow Up**

The subjects will be followed every 6 months following surgery for a total of 2 years. At the time of the first 6 month follow up the subjects receiving metformin will return any unused study drug and drug reconciliation will occur.

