### **Adverse Event Reporting Period**

Adverse events will be reported after the subject begins taking the metformin or starts the observation period. The bronchoscopy and surgery are considered standard of care.

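### The 2-year RFS comparison excludes patients after open allocation, observation has no defined start, and no analysis of all randomised patients is planned

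*Combined protocol and SAP*

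**What the plan says.** Section 7.1 (Statistical Methods) sets the analysis population: "All patients meeting the eligibility criteria, and who started treatment, will be considered evaluable for the 2 year RFS rate endpoint". The RFS rate in each arm is the number alive and recurrence-free at 2 years divided by the number evaluable, and the arms are compared by a chi-squared test. No analysis of all randomised patients, and no sensitivity analysis for those left out, appears anywhere in the document.

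On the order of events, section 6.3 has eligibility checked at Visit 3, and then "if the subject is still eligible they will be randomized and receive their study treatment (metformin or observation". Starting therefore follows randomisation. Under section 5.4, drug is handed over in person: "At the time of the visit it will be distributed by the study team". The control is observation, so the arm is known once the envelope is opened.

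The only other reference to an observation start is in section 8.1 (Adverse Event Reporting Period): "Adverse events will be reported after the subject begins taking the metformin or starts the observation period". Neither section ties that start to an event or a date.

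On numbers, section 3.1 states: "We plan to randomize a total of 100 patients (50 per arm), such that 90 patients are evaluable for the primary endpoint". Section 2 gives the split: "iPS cell lines from the first 20 patients randomized to the metformin arm" and "the remaining 25 patients randomized to metformin and the 45 observation patients".

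**The concern.** Randomisation makes the two groups of 50 comparable. It does not do so for subsets chosen afterwards, when patient and team know the arm. Starting metformin is an act that can be refused or delayed, and section 4.1 also makes a metformin start within 90 days of surgery an eligibility criterion. After randomisation only a metformin patient can fail that criterion. On the natural reading of section 6.3, observation begins at randomisation, so an observation patient could hardly fail to start. The filter is therefore not symmetric as written.

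RFS is one of the two primary objectives. If patients who do not start differ in prognosis from the rest, part of any difference between arms would reflect who was dropped. The direction cannot be known in advance, and no planned analysis would reveal it.

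**Working it through.** **The plan's own counts.** 100 randomised − 90 evaluable = 10 losses. Section 2 implies 20 + 25 = 45 metformin and 45 observation patients, so 50 − 45 = 5 lost per arm. Section 7.1 defines evaluability only by eligibility and starting, so these losses are patients who fail one of those two conditions. Equal counts do not make the remaining groups comparable if the reasons differ.

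**Assumptions, none stated in the documents.** True 2-year RFS p = 60% in both arms (no drug effect), two-sided alpha 0.05, and a chosen RFS q among excluded patients. Section 1.1 gives only a recurrence range of 30–70% with no time point, so p = 50% and 70% are also shown.

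**Formula.** If k of 50 patients with RFS q are excluded, RFS among those left is (50p − kq)/(50 − k). Bias is this value for metformin minus the same value for observation. Error rates come from exact binomial enumeration of the uncorrected chi-squared test.

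Example with p = 0.60, k = 5, q = 0.30: (30 − 1.5)/45 = 63.3%. Observation with average exclusions stays at 60%, so the bias is +3.3 points. The standard error at 45 v 45 is √(0.24 × 2/45) = 10.3 points, so this is about a third of a standard error.

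| Scenario (p = 60%) | Evaluable | Bias (points) | Two-sided error |
|---|---|---|---|
| No exclusions | 50 v 50 | 0 | 5.24% |
| Average prognosis, both arms | 45 v 45 | 0 | 4.86% |
| q = 30%, both arms | 45 v 45 | 0 | 5.16% |
| q = 30% metformin, average observation | 45 v 45 | +3.3 | 6.22% |
| q = 75% metformin, average observation | 45 v 45 | −1.7 | 5.08% |
| 5 metformin lost, q = 30%; none on observation | 45 v 50 | +3.3 | 6.14% |
| 2 metformin lost, q = 30%; none on observation | 48 v 50 | +1.25 | 5.32% |
| Extreme: all 5 excluded metformin patients fail | 45 v 50 or 45 v 45 | +6.7 | 10.13% or 10.25% |

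In the +3.3-point case at 45 v 45, false findings favouring metformin make up 5.10%, against 2.43% with average exclusions and 2.62% at 50 v 50.

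**Other values of p**, at 45 v 45 with q = p/2 among metformin exclusions only:
- p = 50%: (25 − 1.25)/45 = 52.8%, bias +2.8 points, error 5.26% (4.51% with average exclusions).
- p = 70%: (35 − 1.75)/45 = 73.9%, bias +3.9 points, error 7.35% (5.35% with average exclusions).

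**All-randomised analysis of the +3.3-point case.** With complete follow-up, metformin RFS is (45 × 0.633 + 5 × 0.30)/50 = 60%. Bias is 0 and error 4.99%, of which 2.49% favours metformin.

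**The case against.** The filter is narrow. Eligibility is checked at the randomisation visit, drug is handed out there, and patients who start and later stop remain in the denominator. Bias is zero when exclusions have average prognosis, or when equal numbers with equally poor prognosis are lost from both arms. The main adverse case moves the estimate by a third of a standard error. With two non-starters the error is 5.3%, against 5.2% with no exclusions. The trial is a pilot with feasibility listed first, and power is about 34% for an assumed 60% v 75%, so the RFS test cannot be decisive on either set. One can also fairly read section 6.3 as starting observation at randomisation.

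The alternative has a weakness of its own. Under the section 7.1 formula, a patient with unknown status counts in the denominator only. At 60% RFS, five metformin non-starters of average prognosis with unknown status, and none on observation, give 45 × 0.6/50 = 54%. That is a shift of −6.0 points with 9.1% error, larger than the bias being removed. Two such patients give −2.4 points and 5.7%. Section 4.4.2 makes data after withdrawal of consent depend on permission.

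These points stand, and they limit how serious the matter is. They do not remove it. Reading observation as starting at randomisation confirms the asymmetry: metformin patients can fail the filter and observation patients hardly can. The weakness over unknown status argues for following non-starters and showing both sets, rather than for having no all-randomised analysis. Pilot status does not alter the fact that RFS is a primary objective with a planned test.

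**Conclusion.** The point holds and should be fixed, though it is not fatal. The wording of the plan establishes the defect: the only between-arm RFS comparison uses subsets formed after open allocation, observation has no defined start, and no all-randomised analysis is planned. The documents do not show that exclusions will in fact be unbalanced.

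The size depends on assumed RFS and prognosis. Plausible cases at 60% RFS run from −1.7 to +3.3 points, with two-sided error of about 5% to 6%. The extreme bound is +6.7 points and about 10%. If non-starters have average prognosis the bias is zero. Confidence is high in the reading of the text; the magnitudes are illustrations.

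**What to change.** - In section 7.1, make all randomised patients, analysed in the arm assigned, the primary set for 2-year RFS.
- Keep the eligible-and-started set as a sensitivity analysis, and define the observation start as the randomisation date.
- Follow non-starters, where consent allows, on the existing schedule in section 6.5, which is not limited to those who started: "The subjects will be followed every 6 months following surgery for a total of 2 years".
- Report by arm the number and reasons of exclusions, and the number with unknown 2-year status. Present both sets together, because the all-randomised result is itself sensitive to unknown outcomes.

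As a separate wording matter that adds no weight here, section 5.3 places opening of the envelope after consent, while section 6.3 places randomisation at Visit 3. The two should be reconciled.

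**Cost.** No extra patients or visits are needed, only changes of wording and follow-up of non-starters at visits already planned. There is slight dilution. For an assumed 60% v 75% among starters, with non-starters gaining nothing, the 15-point difference becomes 15 × 45/50 = 13.5 points with five non-starters. Power is then about 30% at 50 v 50, instead of about 34% at 45 v 45. With two non-starters it becomes 15 × 48/50 = 14.4 points, and power is about 33% instead of about 35% at 48 v 48.

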### 4.4 Early Withdrawal of Subjects

#### 4.4.1 When and How to Withdraw Subjects

- Subject develops a diagnosis of diabetes
- Failure of subject to adhere to protocol requirements
- Subject decision to withdraw from the study (withdrawal of consent)

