#### 4.4.2 Data Collection and Follow-up for Withdrawn Subjects

Even though a subject has withdrawn from the study, it may be important to collect some follow-up or survival data on such subjects throughout the protocol defined follow-up period. Such data is important to the integrity of the final study analysis since early withdrawal could be related to the safety profile of the study drug. If a subject withdraws consent to participate in the study, for subject safety reasons, attempts should be made to obtain permission to collect follow up information whenever possible.

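### Section 7.1 gives no rule for unknown 2-year status, and its formula, taken literally, counts those patients as failures

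*Combined protocol and SAP*

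**What the plan says.** Section 7.1 sets the denominator in one sentence: "All patients meeting the eligibility criteria, and who started treatment, will be considered evaluable for the 2 year RFS rate endpoint". There are two conditions, and neither concerns follow-up. The rate in each arm is then "the number of patients who are recurrence-free and alive at 2 years divided by the total number of evaluable patients in each arm", reported with a 95% confidence interval and compared by a chi-squared test. The logistic models for the metformin sensitivity index use the same yes/no outcome, including "the interaction between the metformin sensitivity index metrics and treatment on the 2 year RFS status as the outcome of interest".

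On follow-up, section 3.1 says "Patients will be followed for 2 years from the time of surgery to evaluate 2-year RFS", and section 6.5 schedules visits every 6 months over that period. Section 3.1 also says "We plan to randomize a total of 100 patients (50 per arm), such that 90 patients are evaluable for the primary endpoint", without saying why ten would not be evaluable.

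Four places touch on incomplete data:

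- Section 4.4.1 lists "Failure of subject to adhere to protocol requirements" among the reasons for withdrawal.
- Section 4.4.2 says that after withdrawal "it may be important to collect some follow-up or survival data on such subjects". It goes on to tie such data to the integrity of the final analysis, and asks that permission be sought when consent is withdrawn.
- Section 9.1 asks for attempts to secure permission for vital status, as a minimum, when authorization is revoked.
- Section 9.3 requires missing entries on the case report form to be explained.

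None of these is a rule for the analysis.

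**The concern.** The denominator is closed when treatment starts, but the numerator needs a status two years after surgery. A patient last seen recurrence-free at month 8, and not seen again, belongs to the first and cannot be counted in the second. In the arithmetic that patient is the same as a recurrence.

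The 2-year RFS comparison is one of the two primary objectives in section 2, and the introduction says the pilot should help to show whether a phase III trial is feasible and justified. A pilot of this size has limited power, so the arm-level rates and their intervals are likely to be the part carried forward. Those are the quantities that loss to follow-up distorts. Equal loss lowers both arms and shrinks a true difference. Unequal loss biases the comparison against the arm that loses more.

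**Working it through.** **The plan's own figure.** The documents state no significance level, power, target difference or dropout rate, so the sample size has no power basis to reproduce. Only the counts can be checked: 90/(1 − 0.10) = 100, where the 10% is itself inferred from 90 of 100. Section 2 gives 20 + 25 = 45 metformin patients and 45 on observation, so 45 evaluable per arm.

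**A single arm by hand.** Take 45 evaluable patients: 28 known successes, 12 known failures and 5 unknown (assumed).

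- Section 7.1 formula: 28/45 = 62.2%
- Known status only: 28/40 = 70.0%
- All unknowns counted as successes: 33/45 = 73.3%

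Each unknown patient who would have succeeded costs the arm 1/45 = 2.2 points.

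**Assumptions for the rest.** True 2-year RFS is S = 60%, with exponential times and 45 per arm. A share L of patients has a loss time spread evenly over 24 months, unrelated to outcome. Tests are uncorrected chi-squared, two-sided 5%.

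**Estimate.** A success is counted only if the patient is recurrence-free at 2 years and not lost, so the formula gives S × (1 − L). Coverage is by exact binomial enumeration.

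| L | Formula reads | Wilson 95% CI covers 60% in |
|---|---|---|
| 0% | 60% | 95% |
| 5% | 57% | 93% |
| 10% | 54% | 87% |
| 15% | 51% | 77% |

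Simulated Kaplan-Meier estimates with 6-monthly visits at their nominal months read about 60% throughout, with 95% coverage.

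**Dropping the unknowns.** Some patients recur before their loss time, so at L = 10% about 7.8% of the arm has unknown status. The complete-case rate is 0.54/(1 − 0.078) = 58.6%. That is 1.4 points low, against 6 points for the formula.

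**Unequal loss, no true effect.**

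- 10% against 5%: 0.60 × 0.90 − 0.60 × 0.95 = −3 points, rejection 5.5%
- 15% against 5%: 0.60 × 0.85 − 0.60 × 0.95 = −6 points, rejection 8.1%

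With no loss the rejection rate is 4.9%.

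**Unequal loss, true 80% against 60%.**

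- The better arm loses 15%, the other 5%: 0.80 × 0.85 − 0.60 × 0.95 = +11 points, power 19%
- The reverse: 0.80 × 0.95 − 0.60 × 0.85 = +25 points, power 71%

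**Equal loss, true 80% against 60%.** Power of the planned test is 56%, 49.5%, 43% and 37% at 0%, 5%, 10% and 15% loss. A simulated Kaplan-Meier comparison at 2 years gives 53–54%, 51–53%, 51% and 48–49%. The planned test is about 3 points better with no loss, level at 2–3% loss, and worse beyond that.

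**The case against.** **The documents do not prescribe failure coding.** A reader might infer that the plan has chosen to count unknown status as failure. It has not. It is silent, and the failure coding is what follows from using the formula as written.

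**The 90 of 100 may have been meant to cover losses.** Eligibility is re-checked at the randomisation visit (section 6.3, "less than 90 days from the time of surgery) the subject will be seen by the study team"), where treatment is also given. Few randomised patients should then be ineligible or untreated, so the ten could be an allowance for loss to follow-up. On that reading the analysis is effectively complete-case, the error at 10% loss is 1.4 points, and applying loss again to 45 per arm counts it twice. This is a fair reading of 3.1, but the 7.1 definition does not allow it: a treated patient who is later lost remains evaluable. The two sections conflict, and the complete-case reading is also biased, though less.

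**The plan does try to limit loss.** It would be wrong to infer indifference. Sections 4.4.2 and 9.1 encourage follow-up and ask for permission to be sought. They do not secure recurrence status, and they give no analysis rule.

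**The harm may be small.** At 5% equal loss the shift is 3 points, against a standard error of √(0.6 × 0.4/45) = 7.3 points in each arm. Material harm needs roughly 10–15% loss or a 10-point imbalance. This stands.

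**The direction is unknown.** A reader might infer bias against metformin, because withdrawal for non-adherence may fall mainly on that arm. But only metformin patients receive monthly calls (section 6.4), which could improve their retention. The documents do not show which arm would lose more.

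**Kaplan-Meier rests on non-informative loss.** With 15% against 5% loss, RFS 60% on study and a recurrence hazard that doubles or triples after loss, the Kaplan-Meier difference is off by 1.3 or 2.2 points and the planned one by 4.7 or 3.8. The order reverses at about a fourfold hazard. Kaplan-Meier is better under plausible conditions, not always.

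**Conclusion.** The point holds as a gap in section 7.1 that should be fixed: handling of unknown 2-year status is unspecified, and the literal formula treats it as failure. The estimate is biased downward by S × L under loss unrelated to outcome, which is 3, 6 and 9 points at 5%, 10% and 15% loss when true RFS is 60%. The test is distorted mainly when loss differs between arms. With no loss there is no bias.

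The finding about the wording rests on the text alone. The sizes rest on assumed RFS, loss rates and loss pattern, none of which the documents supply. Neither a deliberate failure rule nor a bias in a known direction can be claimed.

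**What to change.** 1. **Section 7.1, estimate.** Estimate 2-year RFS from surgery in each arm by Kaplan-Meier, with recurrence or death as the event and censoring at the last disease assessment. Compare the two 2-year estimates with a 95% confidence interval. The choice of landmark test is open; a complementary log-log test is one option.
2. **Section 7.1, visit timing.** Make the 24-month visit count toward the 2-year landmark, with a stated window, for example by dating results to nominal months. This matters: in simulation with visits within 1 month of schedule, true RFS 60% and 10% loss, nominal dating read 60%. Actual dates read at 24.0 months gave 63%, and at 25 months 39%.
3. **Sensitivity analysis.** Keep the crude proportion with unknown counted as failure, labelled as such.
4. **Index models.** Handle unknown status consistently with the main analysis. A logistic model per visit interval is one way, not a requirement.
5. **Section 4.4.2.** State that recurrence and survival follow-up continues to 2 years in both arms unless the patient refuses it.
6. **Sections 3.1 and 7.1.** Say why 10 of 100 are expected not to be evaluable, and make the two sections agree.

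**Cost.** Wording changes, a visit window, and recording of event and last-assessment dates. No extra patients, visits or follow-up time. About 3 points of power are given up if loss is near zero, 6-monthly visits leave recurrence dates coarse, and the non-informative-loss assumption has to be stated.

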### 1.1 Background

#### Non-small cell lung cancer (NSCLC)

Worldwide, lung cancer remains the leading cause of cancer-related death in men and the second leading cause of cancer-related deaths in women (Jemal et al., 2011). The American Cancer Society estimates an incidence of 221,130 new cases of lung cancer for 2011 with 156,940 deaths (Siegel et al., 2011). Non-small cell lung cancer (NSCLC) accounts for more than 80% of all pulmonary neoplasms with greater than 60% of patients presenting with advanced or metastatic disease at the time of diagnosis [SEER; Little 2007]. Despite having a better chance for cure following surgical resection, even patients with early stage disease have a relatively high

risk of recurrence, with reported local recurrence rates ranging from 13% to 45% for Stage I disease and 17% to 55% for Stage II disease [Kelsey 2009, Lardinois 2005, Goodgame 2009]. Despite advances in screening, targeted therapies, adjuvant chemotherapy, minimally invasive surgery, and stereotactic radiation, the overall approach to lung cancer care has changed little in over 25 years, with relatively minimal improvements in survival.

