#### Metformin for non-small cell lung cancer

Large, phase III randomized studies for evaluating the effects of metformin as a chemoprevention agent are already underway in breast cancer. Although preliminary data suggests a potential effect in non-small cell lung cancer (Memmott RM et al., 2010), no trials addressing the question are yet open and enrolling. The recurrence rate for treated NSCLC ranges from 30-70% based on clinical and pathologic stage. For patients in the Stage IB-IIIA stage categories, adjuvant platinum-based chemotherapy has shown proven benefit with an increase in 5 year survival of 5-13%. Despite this improvement, recurrence rates remain high. Preliminary data has suggested activity of metformin in reducing cancer risk. Because metformin is a generic, inexpensive, well known and generally well tolerated oral agent that is commonly used to treat diabetes (including lung cancer patients who have diabetes), its evaluation as a potential adjuvant treatment for NSCLC can take place in an accelerated fashion. As lung

squamous cell carcinoma commonly affects the proximal airways, in contrast to lung adenocarcinoma, which typically affects more distal airway-alveolar units, the potential to bronchoscopically survey for precursor lesions such as bronchial dysplasia or carcinoma in-situ is feasible. Given this, we will institute the described pilot study protocol to evaluate the feasibility of metformin administration and tissue collection and to characterize the genomic alterations associated with these disease phenotypes under the influence of metformin administration. Interestingly, metformin has been linked to a number of the newly-identified genes identified with significant mutations in lung squamous cell carcinoma, including PTEN, PIK3CA, TP53, TSC1, BRAF, Notch1 and CREBBP. Whether metformin modifies the functional outcome for any of the novel mutations identified in invasive lung squamous cell carcinoma will be addressed in this pilot study.

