### 4.2 Exclusion Criteria

- Currently taking metformin or other diabetic drugs
- Current or previous congestive heart failure, renal failure or liver failure
- Creatinine in Women of 1.4 or greater and Creatinine in Men of 1.5 or greater
- Existing untreated or prior cancer <5 years from diagnosis
- Received neo-adjuvant platinum-based chemotherapy or targeted therapy
- Receiving adjuvant platinum-based chemotherapy or targeted therapy after surgical resection

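### Section 7.1 plans no stage adjustment for the non-randomised comparison of 2-year RFS between metformin-sensitive and not-sensitive patients

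*Combined protocol and SAP*

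**What the plan says.** Section 7.1 (Statistical Methods) estimates the 2-year RFS proportion in each arm, "and compared using a chi-squared test". For the index it states: "Logistic regression models will be used to assess the impact of metformin sensitivity index metrics, treatment, and the interaction" between the two, with 2-year RFS status as the outcome. It also says: "Clinical data regarding recurrence-free survival (RFS) will be utilized for development of the metformin sensitivity index".

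Section 2 (Study Objectives), secondary objective 2, reads "To apply the metformin sensitivity index on the remaining 25 patients randomized to metformin and the 45 observation patients", 70 patients in total, "to compare the 2-year RFS rate between metformin-sensitive and metformin-not-sensitive patients". Section 7.1 writes no separate test for that pooled contrast.

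On stage, Section 1.1 states: "The recurrence rate for treated NSCLC ranges from 30-70% based on clinical and pathologic stage". It also cites "reported local recurrence rates ranging from 13% to 45% for Stage I disease and 17% to 55% for Stage II disease". Section 4.1 admits stages IA to IIIA. Section 6.2 confirms stage at surgery, and Section 6.3 places randomisation at the later Visit 3. Section 5.3 describes numbered envelopes and names no stratification factor.

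**The concern.** Sensitive and not-sensitive patients are defined by a patient characteristic, so randomisation does not balance stage between them. If they differ in stage, part of any RFS difference between them would be a stage difference, and the plan has no prespecified way to see or remove it. Stage is known before randomisation, and the protocol itself describes it as prognostic, so it is the natural first adjustment. Adding it only after the results are known would be discretionary.

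The quantity at stake is the pooled sensitive versus not-sensitive contrast and, in the logistic model, the index coefficient.

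**Working it through.** **Inputs from the documents.** Section 3.1: 100 randomised, 90 evaluable. Section 2: 20 + 25 = 45 metformin patients, and 25 + 45 = 70 patients in the index contrast. These counts agree with each other. The documents give no power, effect size, alpha or 2-year RFS by stage, so there is no planned figure to reproduce.

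**Assumptions.** Two strata, stage I and stage II-IIIA; 60% stage I overall; index groups of 35:35 or 23:47; two-sided 5% tests; no true index effect. Three sets of 2-year RFS rates are used:
- (a) RFS of 70/60/50/40/30% for IA, IB, IIA, IIB and IIIA, spreading the 30-70% recurrence range evenly. Stage I: (70 + 60)/2 = 65%. Stage II-IIIA: (50 + 40 + 30)/3 = 40%.
- (b) An upper bound: 70% vs 30%.
- (c) Midpoints of the quoted local recurrence ranges. Stage I: 100 - (13 + 45)/2 = 71%. Stage II, applied to II-IIIA: 100 - (17 + 55)/2 = 64%.

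**Step 1: false difference.** It equals the gap in stage I share times the RFS gap between strata.
- Gap of 20 points: (a) 0.20 × 25 = 5.0 points; (b) 0.20 × 40 = 8.0; (c) 0.20 × 7 = 1.4.
- Gap of 10 points: (a) 2.5; (b) 4.0; (c) 0.7.

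**Step 2: false-positive rate of the pooled contrast** (simulated samples of 70, chi-squared test without continuity correction, against a Cochran-Mantel-Haenszel (CMH) test by stage).

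| Gap in stage I share | (a) | (b) | (c) | Stratified |
|---|---|---|---|---|
| None | 4.4-5.3% across (a)-(c) | | | about 5% |
| 10 points | 4.9-5.2% | 5.6-5.8% | 5.2% | about 5% |
| 20 points | about 6.4% | about 9.2% | about 5.2% | about 5% |

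**Step 3: chance imbalance.** With no index-stage link, a gap of 20 points or more still arises in 11-12% of samples at 60% stage I. This falls to about 4-5% at 80% stage I and about 1% at 90%. It is already included in the 4.4-5.3% overall rate.

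**Step 4: interaction.** With a 20-point stage gap common to both arms, the index-by-treatment log-odds ratio moves by at most 0.012. The median standard error of that term is above 1.0, so this is negligible.

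**Step 5: arm comparison, 45 per arm.** Stratifying by stage changes power by -1.7 to +7.7 points for a 20-point benefit and by -1.0 to +2.9 for a 10-point benefit. Under (a) with 40-70% stage I and a 20-point benefit, the change is -0.6 to +2.4 points once both tests are set to 5% size.

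**Step 6: what two levels leave behind.** If the index shifts patients across all five stages under (a), with a 20-point stage I gap, two-level adjustment cuts the false difference from 6.3 to 1.3 points, a reduction of about 79%. It does not reach zero.

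**The case against.** The strongest objection is that no index-stage link is shown. The index is built on iPS lines (Section 2) reprogrammed from skin fibroblasts (Section 3.2), not on tumour. That stands. The only route the documents suggest is indirect: RFS data are used to develop the index, so it may partly track stage. Adjusting the later contrast does not correct that development step.

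Second, 20 points is an arbitrary gap, and 10 points barely moves the error rate. This stands too, as does the result under (c), the only set built on stage-specific figures in the documents. Set (c) uses local recurrence only, however, so it may understate the effect of stage.

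Third, enrolment may lean to lower stages. Section 4.2 excludes patients "Receiving adjuvant platinum-based chemotherapy or targeted therapy after surgical resection", while Section 1.1 credits platinum chemotherapy with benefit in stages IB-IIIA. Chance gaps would then be rarer.

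Fourth, Section 7.1 already plans frequencies and percentages for categorical variables. That is true, but it does not name stage or index group.

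A reader might go further and infer that the primary arm comparison is biased. The documents do not support this: the arms are randomised, and the chi-squared test is valid and unbiased on average. Its evaluable set is limited to eligible patients who started treatment, so the protection of randomisation is not complete, but that is separate from stage. Nor do the documents support the inference that the interaction test is distorted; a stage gap common to both arms hardly affects it.

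**Conclusion.** The omission is real and affects one analysis: the pooled sensitive versus not-sensitive comparison in secondary objective 2. Its size depends on an index-stage association that the documents do not show. With none, the overall false-positive rate is about 4.4-5.3%. With a systematic 20-point gap, the false difference is about 1.4 to 8 points and the rejection rate about 5-9%, against about 5% when stratified. With a 10-point gap, the rejection rate is about 5-6%.

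These figures rest on an assumed 60% stage I and on assumed stage-specific RFS. The 30-70% recurrence range carries no time horizon and is not specific to resected squamous disease. It should not be read as 2-year recurrence in this population.

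In a pilot this is a modest, optional improvement. It is worth making because the data are already collected and prespecification removes discretion.

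**What to change.** In Section 7.1:
1. State that 2-year RFS will be compared between metformin-sensitive and not-sensitive patients with adjustment for pathologic stage in two levels (for example I vs II-IIIA). Use either a Mantel-Haenszel risk difference with 95% CI and a CMH test, or a logistic model with index group, treatment and stage.
2. Include the same stage term in the index logistic model. This alone is not enough: with the interaction in the model, the index coefficient is not the pooled contrast, so step 1 is needed as well.
3. Tabulate stage by index group and by arm.
4. Keep the unadjusted chi-squared test as the primary arm comparison. A stage-stratified CMH result beside it is optional and supportive.

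Cost: a few sentences and no new data. Standard errors of the index and interaction terms rise by 2-3% under (c), 5-7% under (a) and 10-13% under (b). For a true 25-point pooled index difference, power changes by between -3.0 points (c) and +8.5 points (b), so there is a small loss if stage is weakly prognostic. Residual confounding remains, as does any influence of stage on index development.
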